The target population includes WHO Grade 2, Grade 3, and Grade 4 gliomas. The median survival for each of these tumors is approximately 10-15 years, 2-7 years, and 20 months, respectively. WHO Grade 4 gliomas (median OS ~20 months) are included in this study to address the safety of this agent.

Ultimately, long term treatment could be most beneficial for those with WHO Grade 2-3 tumors where the sleep-fatigue symptom cluster is a significant problem for long term survivorship.

Furthermore, these pilot data will not only inform subsequent drug development of solriamfetol in this population but also in other cancer patients receiving or having completed chemo-radiotherapy, in neurologically diseased patients taking antiepileptics, or patients prescribed corticosteroids.

6. Estimated Study Length

Anticipated Enrollment Duration: 18 months

Anticipated Treatment Duration: 24 months (18 month enrollment + 6 month on and post-treatment follow up)

Total Study Duration from first patient enrollment to end: 2 years

Anticipated Patient Enrollment per month: 2

Total Anticipated Patient Enrollment: 36

7. Interim Analysis Plan

Interim analysis of safety data will be performed when all 36 evaluable patients have completed dose escalation. Interim analysis of secondary efficacy endpoints is not planned.

References

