The mean MWT sleep latency decreased by 12.1 minutes from week 4 to week 6 in patients who were switched to placebo during the Double-Blind Withdrawal Phase compared with a change of -1.0 minute for those who remained on solriamfetol ($p<0.0001$). Mean ESS scores increased by 4.5 among patients who were switched to placebo during the Double-Blind Withdrawal Phase, compared with a mean decrease of 0.1 for those who stayed on solriamfetol ($p<0.0001$).

More AEs occurred during the Titration Phase (48.9%) than during the Stable Dose Phase (10.2%). The most common AEs ($\geq 5\%$) during the Titration Phase were headache, dry mouth, nausea, dizziness, and insomnia.

6. Summary of Study Rationale

In summary, sleep dysfunction is common in brain tumor patients and clusters with fatigue, neurocognitive dysfunction, and poor quality of life. Widespread alterations in neurotransmitters and cytokine signaling suggest a need to intervene with an agent that targets neurotransmitter signaling as opposed to daytime stimulants (e.g. methylphenidate) or circadian agents (e.g. melatonin). The combined dopaminergic and noradrenergic activity of solriamfetol set it apart from other agents (e.g. modafinil) that have been previously tested and have shown signals of activity on this symptom cluster. Existing therapeutic studies caution against early efficacy studies until safety is determined given the potential for antiepileptic drug and corticosteroid drug-drug interactions, sensitivity of these patients to psychoactive agents, risk of increasing seizure activity, and the susceptibility of this population to drug-induced cognitive dysfunction.

Solriamfetol is an ideal agent for testing. The drug's combined norepinephrine and dopamine reuptake inhibitor properties are attractive in glioma patients who have widespread neurotransmitter dysfunction and a symptom cluster that includes impairments in fatigue, mood, and neuro-cognition.^{40,44}

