This is a single-arm, open label, two-part safety study of solriamfetol in patients with WHO grade 2-4 gliomas. Patients with stable disease by clinical examination and neuroimaging who have an ESS \geq 10 and meet all inclusion/exclusion criteria will be recruited and enrolled. First, all patients will receive solriamfetol at escalating doses. Second, all patients will complete a fixed dose drug continuation treatment at the patient-specific maximum tolerated dose.

The study will occur in 3 phases:

Open Label Safety Study of Solriamfetol to Promote Wakefulness and Improve Cognition and Quality of Life in
Patients with Primary Gliomas
Wake Forest Baptist Comprehensive Cancer Center
WFBCCC 98418

1. Pre-Treatment Baseline (~1 week)
2. Flexible Dose Titration (~3 weeks)
3. Fixed Dose Drug Continuation (~6 weeks)

Patients will initially complete a 1-week baseline actigraphy and sleep diary prior to treatment initiation to establish a baseline sleep pattern.

Solriamfetol will be dosed by flexible dose titration starting at 75 mg daily in all patients and escalating after 7 days (1 week) to 150 mg daily and then after 7 days to 300 mg daily for a total duration of 3 weeks (flexible dose titration period). Patients who experience a dose-limiting toxicity will be de-escalated to the last tolerated dose level and move to the fixed dose drug continuation phase. Prior studies incorporating this design have used a 3-day treatment prior to escalation.⁴⁹ For this study, 7 days has been selected to provide a sufficient period of time to observe both immediate and delayed toxicities that could be seen in this population.

Following completion of the flexible dose titration, patients will continue solriamfetol at 300 mg daily or their maximally tolerated dose for a treatment duration of 6 weeks. For this period of the study, 8 weeks has been selected to allow for time to observe both short term improvement in patient-reported sleep as well as potentially more delayed changes in other study endpoints (i.e. fatigue, mood, neurocognition).

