The main study assessments will be performed at baseline prior to flexible dose titration and then at the end of the fixed dose drug continuation phase. This will include: (1) patient reported measures, (2) objective measures of sleep activity, (3) neurocognitive functioning (4) assessment of associated symptoms such as fatigue, mood, and (5) quality of life. Additional assessment of patient-reported measures will be performed after dose escalation and prior to the fixed dose drug continuation. Due to practice effects and other issues related to repeated measurement, neurocognitive data will only be collected pre- and post-treatment.

Sleep diaries will be completed continuously throughout the ~10 week study. Seven-day actigraphy will be completed at each dose escalation and during the first and last weeks of fixed dose drug continuation.

Additional assessments will be performed as per the standard of care. In this population, it is standard of care for MR Brain to be performed roughly every 8-16 weeks. Data on tumor status by imaging (e.g. stable disease, imaging progression, etc) will be recorded prior to study treatment and following study treatment to assess for tumor progression as a factor contributing to changes in patient-reported and clinician assessed outcome measures.

Adverse events will be assessed every 7 days during flexible dose titration (via telephone) and at the end of the fixed dose treatment. Adverse event data will be compared to that reported in patients with narcolepsy.⁵⁰

Open Label Safety Study of Solriamfetol to Promote Wakefulness and Improve Cognition and Quality of Life in
 Patients with Primary Gliomas
 Wake Forest Baptist Comprehensive Cancer Center
 WFBCCC 98418

2. Study-Related Activities

	Pre-Study ^a ^k	Baseline Visit V1 (D1)	Begin Flexible Dose Titration (D8+1 dy)	Flexible Dose D7 (D15+1 dy)	Flexible Dose D14 (D22+1 dy)	Fixed Dose Initiation Visit V2 ^k (D29+7 dys)	End of Treatment Visit V3 (D70+7 dys)	30 day Follow Up Visit V4 ^k
Informed consent	X							
Demographics	X							
Medical history	X							
Concurrent meds	X					X	X	
Physical exam ¹		X				X	X	X
Vital signs ^b	X ^c	X				X	X	X
CBC w/diff, platelets	X					X	X	X
Serum chemistry ^d	X					X	X	X
B-HCG ^e	X							
Electrocardiogram (EKG)		X				X		
Adverse event evaluation		X	X ^f	X ^f	X ^f	X	X	X
Epworth Sleepiness Scale (ESS)	X	X ^g	X ^g	X ^g	X ^g	X ^g	X ^g	
Sleep Measures: Sleep diary, Actigraphy ^h		X ⁱ	X	X	X	X	X	

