Pittsburgh Sleep Quality Index (PSQI)		X				X	X	
Associated Symptom PROMs: BFI, CFS, BDI		X				X	X	
QOL PROMs: FACT-Br		X				X	X	
Neuro-cognitive Battery		X					X	
Standard of Care MR Brain ^a	X						X ^j	

¹ Patient's undergoing telehealth assessment at the pre-screening timepoint require virtual examination by observation only. Blood draw and laboratory testing can be performed locally and reviewed remotely.

^a Pre-study requirements listed in table must be completed **within** 21 days prior to registration.

^b Blood pressure (mmHg), heart rate (BPM)

^c Height, Weight, M² Patients undergoing telehealth assessment can provide this information verbally using home device (e.g. scale).

^d Albumin, alkaline phosphatase, total bilirubin, bicarbonate, BUN, calcium, chloride, creatinine, glucose, potassium, total protein, SGOT[AST], SGPT[ALT], sodium.

^e Serum pregnancy test (women of childbearing potential).

^f May be performed by telephone.

^g Epworth Sleepiness Scale (ESS) will be completed either in the clinic (D1, D29, D70) at each of the study visits (V1, V2, V3) or by telephone (D8, D15, D22) during the flexible dose escalation portion of the study.

^h 7-day sleep diary is to be completed at baseline (D1-7), continuously during dose escalation (D8-14, D15-21, D22-28), and during the first and last week of fixed dose drug continuation (~D29-35 and ~D63-70). Actigraphy will be collected continuously.

ⁱ Patients may complete the baseline sleep diary and actigraphy prior to the Baseline Visit (V1) or after the Baseline Visit (V1).

^j Post-treatment MR Brain is to be performed D85 \pm 42 days.

^k Study visits may be conducted via telehealth visit. Blood draw and EKG (when appropriate) can be performed locally and reviewed remotely.

3. Screening

Glioma patients seen at the Wake Forest Baptist Medical Center will be considered for eligibility at or before their scheduled visits. In general, patients may be approached at the time of routine outpatient visit for follow up with neuro-oncology, medical oncology, radiation oncology, and neurosurgery.

Patients who are identified as potential study candidates will have an opportunity to hear about the study and complete written informed consent. Patients who sign informed consent and do not meet eligibility criteria will be considered screen failures, will not be evaluable for the primary endpoint, will not count toward the total sample size, and this enrollment will be replaced.

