Based on our prior cross-sectional study, we anticipate 30% of patients to be enrolled during adjuvant therapy (i.e. receiving oral chemotherapy), 30% during post-adjuvant surveillance (i.e. not receiving any prescribed antitumor therapy), and approximately 30% during post-recurrent disease treatment (i.e. undergoing salvage treatment with chemotherapy). This will allow for comparisons of toxicity, tolerability, and activity by timing during cancer care.

We anticipate that approximately 20-30% of patients will be taking active corticosteroids and 60% of patients will be prescribed an antiepileptic agent. This will allow us to explore differences in tolerability and activity by these important treatment parameters.

Screening assessments may be completed by telehealth visit. These will be done through MWH when able. If not able, Doximity will be used which is what is done clinically for these patients.

4. Pre-Treatment Baseline

All patients who complete written informed consent and meet eligibility criteria will be registered and will proceed with study treatment. For patients who complete consent at the time of a regularly scheduled visit they can be provided with a baseline sleep diary and actigraph device to complete the Pre-Treatment sleep diary and actigraphy prior to Visit 1 (V1). For patients who elect to take consider study enrollment and return at a later date, sleep diary and actigraphy can be completed after (in the first 7 days after) Visit 1 (V1).

Enrolled patients will complete the pre-treatment study assessments (Section 6.7). Patients will be instructed to complete a 1-week pre-treatment baseline assessment with 7-day sleep diary that records time in bed, time awake, and estimated hours of sleep among other items (Appendix Q) as well as 7-day actigraphy (see Section 7.8.2).

Patients will either return to clinic or receive a telephone call from the study nurse, study coordinator, or study team at the end of this pre-treatment baseline week (Day 7+1 day) to record the completion of pre-treatment baseline actigraphy and sleep diary.

Baseline visit will be performed in-person.

5. Flexible Dosing Titration

Upon completion of pre-treatment baseline assessments, patients will begin flexible dosing titration. All patients will begin solriamfetol 75 mg p.o. once daily. The dose will be titrated every

7 days (+1 day) to 150 mg daily and then 300 mg daily unless the patient experiences symptomatic dose-limiting toxicity.

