Storage Requirements: solriamfetol tablets are to be stored at room-temperature conditions, 15°C to 30°C (59°F to 86°F).

Stability: Studies are ongoing to monitor the stability of solriamfetol tablets.

12 Data Management

Informed consent document	EPIC
Protocol registration form	OnCore
Adverse Events Log (Appendix E)	OnCore
Patient Drug Diary (Appendix F)	
Fixed Dose Patient Drug Diary (Appendix G)	
Epworth Sleepiness Scale (Appendix H)	
Pittsburgh Sleep Quality Index (Appendix I)	
Brief Fatigue Inventory (Appendix J)	
Cancer Fatigue Scale (Appendix K)	
Beck's Depression Inventory (Appendix L)	
Neurocognitive Battery Form (Appendix M)	
FACT-Br (Appendix N)	
Concurrent Medication (Appendix O)	OnCore
Off-Study Form (Appendix P)	OnCore
MR Imaging Record (Appendix Q)	
Sleep Diary and Actigraphy Record (Appendix R)	
Glioma History (Appendix S)	

13 Statistical Considerations

This is a single-arm, open label, non-randomized safety study in patients with stable glioma disease. The primary outcome is safety of oral solriamfetol as doses of 75 mg daily, 150 mg daily and 300 mg daily. Secondary outcomes include ESS score, PSQI score, a composite neurocognitive battery score, FSS score, BDI score, and FACT-Br score.

1. Analysis of Primary Objective

For the primary outcome, NCI Common Terminology Criteria for Adverse Events (CTCAE) version 5.0 will be used for scoring toxicity and adverse events.

The severity and frequency of toxicity and adverse events for each dose of solriamfetol will be tabulated using descriptive statistics. The proportions of subjects who experienced grade 3 or above toxicities will be estimated, along with 95% confidence intervals by each type of toxicity.

To compare the safety of solriamfetol at 75 mg daily, 150 mg daily, 300 mg daily, chi-squared statistics will be used. If there are some cells with expected value <5 , Fisher's exact test will be used for the comparison.

2. Analysis of Secondary Objective

For the secondary outcomes, descriptive statistics will be performed for each of the outcome measures. Changes in pre- and post-treatment scores will be assessed and compared using the pair-t tests if the changes follow a normal distribution and using the Wilcoxon signed rank tests if the changes do not follow a normal distribution. For the comparison between the change in ESS score in the study patients and the published change score in patients with obstructive sleep apnea, we will use the one sample t-test for this comparison.

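### Labs, blood pressure, heart rate and EKG are not scheduled in the 75 mg and 150 mg weeks, so the by-dose comparison in 13.1 under-counts asymptomatic measured events at those doses

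*Combined protocol and SAP*

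**What the plan says.** Section 13.1 (Analysis of Primary Objective) states: "The severity and frequency of toxicity and adverse events for each dose of solriamfetol will be tabulated using descriptive statistics". It continues: "To compare the safety of solriamfetol at 75 mg daily, 150 mg daily, 300 mg daily, chi-squared statistics will be used", with Fisher's exact test where expected counts are small. It gives no rule for assigning a finding to a dose, no denominator of patients measured at each dose, and no time window.

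Section 7.1 describes one week each at 75, 150 and 300 mg, after which "patients will continue solriamfetol at 300 mg daily or their maximally tolerated dose for a treatment duration of 6 weeks". On follow-up it says: "Adverse events will be assessed every 7 days during flexible dose titration (via telephone) and at the end of the fixed dose treatment".

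The 7.2 schedule places the on-study measurements as follows:

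- CBC and chemistry: pre-study, V2, V3, V4.
- Blood pressure and heart rate: pre-study, V1, V2, V3, V4.
- EKG: V1 and V2 only.

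None has an entry at D8, D15 or D22. For adverse events at those three contacts, footnote f reads "May be performed by telephone", and 7.5 makes them telephone calls. The script in Appendix T asks about symptoms. Under 7.5 the dose goes up each week "unless the patient experiences symptomatic dose-limiting toxicity", whereas 7.9.1 also counts abnormal laboratory values as possible DLTs.

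**The concern.** Dose-specific safety is the primary objective (3.1 and section 6), and 13.4 says the results should inform a later randomized study. A by-dose table is informative only if events had a similar chance of being found at each dose. For events that only a measurement reveals, that chance is close to nil at 75 and 150 mg and much higher at 300 mg. A reader could take the lower doses to be clean, or see a dose gradient that does not exist. An abnormality that began at a lower dose and persisted would first be seen at V2 and could be assigned to 300 mg.

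A related imbalance affects symptomatic events. They are asked about weekly at every dose during titration, but 13.1 sets no window, so a patient who stays on 300 mg can accrue about seven weeks of events there against one week at each lower dose.

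**Working it through.** The plan states no figure for this point, so there is none to reproduce.

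**Schedule against dose.** With the first dose on D8, 75 mg covers D8-14, 150 mg D15-21 and 300 mg D22-28. The D15 and D22 calls close the first two weeks, and V2 (D29) follows the third. Scheduled labs, vital signs or EKG in the escalation weeks are therefore 0 of 36 patients at 75 mg, 0 of 33 at 150 mg and up to 30 of 30 at 300 mg. For the EKG, V2 is the only on-drug reading. The exception is patients de-escalated after a DLT, who are measured at a lower dose: a small group selected for toxicity at a higher one.

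**Inputs.** Denominators 36/33/30 and two-sided alpha 0.10 come from 13.4 (13.1 states no alpha). Assumptions: one test per event term, the same true rate at every dose, events assigned to the dose at detection, and the three groups treated as independent, as 13.1 does. At V2, three patients are measured on 75 mg (33 − 30 = 3), m on 150 mg (0 to 6) and 30 − m on 300 mg.

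**Method.** Three-group Fisher (Freeman-Halton) test, summing exact binomial probabilities over tables with p < alpha and the highest rate at 300 mg.

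With no events at 75 or 150 mg, p = 0.303 for one event at 300 mg, 0.090 for two and 0.026 for three. Two events are enough at alpha 0.10.

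Chance of a false gradient peaking at 300 mg, with no unscheduled detection:

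| True rate | m = 0 | m = 3 | m = 6 | Equal detection |
|---|---|---|---|---|
| 1% | 3.5% | 2.8% | 2.2% | 1.9% |
| 2% | 11.4% | 9.1% | 7.0% | 3.4% |
| 5% | 39.1% | 31.3% | 24.1% | 3.7% |
| 10% | 69.0% | 56.9% | 44.4% | 3.3% |

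**Sensitivity.**

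- Nobody measured on 75 mg: 55.5-81.6% at a 10% rate.
- Documented rates (the adverse reaction table in 10.1): hypertension 6/573 = 1.0%, blood pressure increased 7/573 = 1.2%, heart rate increased 8/573 = 1.4%. With none or three measured on 75 mg, these give 2.4-6.6%.
- Unmeasured patient-doses detected at 25% of the full rate, true rate 10%: 21.2-38.1%. At 50%: 10.9-17.2%.
- Alpha 0.05, true rate 10%, no unscheduled detection: 26.3-52.0%.
- Test on any AE, assuming 40% symptomatic at each dose: 300 mg becomes 0.40 + 0.60 × 0.10 = 46%. The false gradient is 9.6%, against 3.4% at 40/40/40.

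**Exposure time, symptomatic events.** Assume a 2% weekly risk at every dose.

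- Constant risk over seven weeks at 300 mg: 1 − 0.98^7 = 13.2% cumulative, false gradient 61%.
- Later weeks at 0.21 of the risk: 1 − 0.98 × (1 − 0.02 × 0.21)^6 = 4.4% cumulative, false gradient about 13.5%.
- Equal 7-day windows: 3.4%.

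The ratio 0.21 is 10.2/48.9, from the AE percentages in the stable-dose and titration phases of the OSA withdrawal study (1.5.2). Those phases had different dose mixes, so it is illustrative. Extra weeks at 75 or 150 mg after de-escalation are ignored.

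**The case against.** The strongest reply is about size. The only documented rates for measured events are 1.0-1.4%, where the test is barely disturbed, and they are 12-week incidences, so one check after a week at 300 mg might find fewer. The large figures need assumed rates of 5-10%. The likeliest source is laboratory abnormalities under chemotherapy, and those patients are also the likeliest to have routine blood tests; Appendix D requires every AE to be entered. For that setting the partial-detection range of 11-38% is more realistic than 44-69%. This stands, and it limits what can be claimed about the test.

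Second, 13.4 sizes the primary analysis on the combined doses and calls the study mainly descriptive, and no stopping or go/no-go rule uses the three-dose test. That is true, but the descriptive by-dose table is itself what misleads.

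Third, symptom-led titration is deliberate, and checking at 300 mg looks at the expected worst case. That is a fair defence of the schedule but not of a by-dose comparison built on it.

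Fourth, the weekly diary in Appendix F records dose and date, and 13.7 plans a safety look after titration. Both help with symptomatic events, but neither changes the final 13.1 comparison.

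Finally, the 61% figure assumes constant weekly risk, which the OSA phase data do not support; about 13.5% is the better guide. The test also treats the same patients at three successive doses as independent groups. That is a separate weakness, which equal windows do not cure.

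**Conclusion.** The concern holds. Followed as written, 13.1 produces a by-dose table and test biased for asymptomatic laboratory, vital-sign and EKG events, because scheduled measurement at 75 and 150 mg is absent except in patients de-escalated after a DLT. The schedule reading is certain. The size is not, since it depends on event rates and routine-care detection that the documents do not give. At the documented rates the damage is mainly a misleading table. For common events the test can mislead as well. The unequal exposure time is a second, related defect of the same comparison and reaches symptomatic events. This should be corrected because by-dose safety is the primary objective and the correction is cheap.

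**What to change.** In 13.1:

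1. Limit the between-dose test to AEs elicited by the weekly contact (V2 for the last week) with onset in each patient's first 7 days at 75, 150 and 300 mg, assigned to the dose taken at onset.
2. Report AEs from the fixed-dose phase, and from any 7 days at a reduced dose after a DLT, separately.
3. Report asymptomatic laboratory, vital-sign and EKG findings as cumulative post-baseline incidence (V2, V3 and V4 where scheduled, noting that V4 is after treatment; EKG at V2 only). List the dose at detection and make no between-dose test. In any by-dose display of these findings, use as denominator the patients actually measured at that dose.

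A minor addition to 7.9.1: state that laboratory DLTs are not screened for before escalation, in line with the symptomatic rule in 7.5.

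The cost is wording in 13.1 and one sentence in 7.9.1, with no new visits or tests. The study gives up any by-dose claim for asymptomatic measured events, and fixed-phase AEs drop out of the between-dose test.
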